4. ANALYSIS POPULATIONS

Population	Definition / Criteria	Analyses Evaluated
Screened	
 All participants who were screened for eligibility 	
 Study Population
Enrolled	
 All participants who passed screening and entered the study. Note screening failures (who never passed screening even if rescreened) and subjects screened but never enrolled into the study (Reserve, Not Used) are excluded from the Enrolled population as they did not enter the study. 	
 Study Population
All Treated	
 All eligible subjects who receive at least 1 dose of study treatment. An incorrect treatment schedule or drug administration or an early termination of treatment will not result in exclusion of subjects from this population. Sub-populations: 
 Part 1: all Part 1 subjects of All Treated population. Note, subjects in Part 1 are exclusively multiple myeloma patients. (2.5 mg/kg will be included in Part 1) Part 2 MM: all Part 2 MM subjects of All Treated population All Treated MM: comprise of subjects in Part 1 and Part 2 MM. Part 2 NHL: all Part 2 lymphoma subjects of All Treated population. 	
 Study Population Safety Efficacy
Evaluable (MM)	
 This population is a subset of the 'All Treated' population, who were initially treated at RP2D in the expansion cohort and have at least two post-baseline disease assessments or they have progressed or died or permanently discontinued treatment. 	
 futility analyses of MM Expansion cohort only

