1.0031	Enrolled	NS1	Summary of Number of Participant by Country and Site ID (NHL)	Include columns: No Treatment, Part 2 NHL, Total column will be the subjects enrolled to NHL cohort. Add a footnote: This summary is based on all subjects enrolled into lymphoma cohorts.	SAC
1.0050	All Treated	IE1	Summary of Inclusion/Exclusion Criteria Deviations (Part 1)	Report for: Part 1, (Summarize: by ascending dose level, Total).	SAC [A]
1.0051	All Treated	IE1	Summary of Inclusion/Exclusion Criteria Deviations (Part 2 MM)	Report for: Part 2 MM, (Summarize: only for 3.4 MM).	SAC [A]
1.0052	All Treated	IE1	Summary of Inclusion/Exclusion Criteria Deviations (All Treated MM)	Report for: All Treated MM, (Summarize: Total).	SAC [A]
1.0053	All Treated	IE1	Summary of Inclusion/Exclusion Criteria Deviations (Part 2 NHL)	Report for: Part 2 NHL, (Summarize: only for 3.4 NHL).	SAC

Study Population Tables					
No.	Population	IDSL / Example Shell	Title	Programming Notes	Deliverable [Priority]
Protocol Deviation					
1.0040	All Treated	DV1	Summary of Important Protocol Deviations (Part 1)	Report for: Part 1, (Summarize: by ascending dose level, Total).	SAC [A]
1.0041	All Treated	DV1	Summary of Important Protocol Deviations (Part 2 MM)	Report for: Part 2 MM, (Summarize: only for 3.4 MM).	SAC [A]
1.0042	All Treated	DV1	Summary of Important Protocol Deviations (All Treated MM)	Report for: All Treated MM, (Summarize: Total).	SAC [A]
1.0043	All Treated	DV1	Summary of Important Protocol Deviations (Part 2 NHL)	Report for: Part 2 NHL, (Summarize: only for 3.4 NHL).	SAC
Population Analysed					
1.0060	Enrolled	SP1	Summary of Study Populations (MM)	Report for: Part 1, (Summarize: by ascending dose level, Total). This table is based on subjects enrolled to MM, we do not have screen failure data, hence no screened population. For columns, include No Treatment, No Treatment for Part 1, No Treatment for Part 2 MM, Dose levels in part 1, All Treated in Part 1, All Treated in Part 2, All Treated and Total. Rows: include Enrolled, Part 1, Part 2 MM, All Treated MM, DLT Evaluable, PK, PD	SAC [A]
1.0061	Enrolled	SP1	Summary of Study Populations (NHL)	Report for: Part 2 MM, (Summarize: only for 3.4 MM). This table is	SAC

Study Population Tables					
No.	Population	IDSL / Example Shell	Title	Programming Notes	Deliverable [Priority]

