3.0593	All Treated	ESI1	Summary of Characteristics of Neutropenia (Part 2 NHL)	Report for: Part 2 NHL, (Summarize: only for 3.4 NHL). Summary based on both all subjects and subjects with events.	SAC
3.0860	All Treated	ESI2b	Summary of Onset and Duration of the First Occurrence of Neutropenia (Part 1)	Report for: Part 1, (Summarize: by ascending dose level, Total). Time of onset: 1-21, 22-42, 43-63, >63. Duration till resolution: 1-21, 22-42, >42.	SAC [A]
3.0861	All Treated	ESI2b	Summary of Onset and Duration of the First Occurrence of	Report for: Part 2 MM, (Summarize:	SAC [A]

CONFIDENTIAL

BMA117159

Safety: Tables					
No.	Population	IDSL / Example Shell	Title	Programming Notes	Deliverable [Priority]
			Neutropenia (Part 2 MM)	only for 3.4 MM) Time of onset: 1-21, 22-42, 43-63, >63. Duration till resolution: 1-21, 22-42, >42.	
3.0862	All Treated	ESI2b	Summary of Onset and Duration of the First Occurrence of Neutropenia (All Treated MM)	Report for: All Treated MM, (Summarize: Total). Time of onset: 1-21, 22-42, 43-63, >63. Duration till resolution: 1-21, 22-42, >42.	SAC [A]
3.0863	All Treated	ESI2b	Summary of Onset and Duration of the First Occurrence of Neutropenia (Part 2 NHL)	Report for: Part 2 NHL, (Summarize: only for 3.4 NHL) Time of onset: 1-21, 22-42, 43-63, >63. Duration till resolution: 1-21, 22-42, >42.	SAC
3.0550	All Treated	OAE07	Summary of Hematologic Toxicity by Preferred Term and Maximum Grade (Part 1)	Report for: Part 1, (Summarize: by ascending dose level, Total).	SAC [A]
3.0551	All Treated	OAE07	Summary of Hematologic Toxicity by Preferred Term and Maximum Grade (Part 2 MM)	Report for: Part 2 MM, (Summarize: only for 3.4 MM)	SAC [A]
3.0552	All Treated	OAE07	Summary of Hematologic Toxicity by Preferred Term and Maximum Grade (All Treated MM)	Report for: All Treated MM, (Summarize: Total).	SAC [A]
3.0553	All Treated	OAE07	Summary of Hematologic Toxicity by Preferred Term and Maximum Grade (Part 2 NHL)	Report for: All Treated MM, (Summarize: Total).	SAC
3.0540	All Treated	ESI1	Summary of Characteristics of Hematologic Toxicity (Part 1)	Report for: Part 1, (Summarize: by ascending dose level, Total). Summary based on both all subjects and subjects with events.	SAC [A]
3.0541	All Treated	ESI1	Summary of Characteristics of Hematologic Toxicity (Part 2 MM)	Report for: Part 2 MM, (Summarize: only for 3.4 MM). Summary based	SAC [A]

Safety: Tables					
No.	Population	IDSL / Example Shell	Title	Programming Notes	Deliverable [Priority]

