3.0352	All Treated	OLB9B	Summary of Coagulation Grade Changes from Baseline Grade (All Treated MM)	Report for: All Treated MM, (Summarize: Total). Produce only for lab tests that are graded. For laboratory tests that are graded for both low and high values, summaries will be done separately and labeled by direction.	SAC [A]
3.0353	All Treated	OLB9B	Summary of Coagulation Grade Changes from Baseline Grade (Part 2 NHL)	Report for: Part 2 NHL, (Summarize: Total). Produce only for lab tests that are graded. For laboratory tests that are graded for both low and high values, summaries will be done separately and labeled by direction.	SAC

Safety: Tables					
No.	Population	IDSL / Example Shell	Title	Programming Notes	Deliverable [Priority]
ECG					
3.0370	All Treated	EG1	Summary of ECG Findings (Part 1)	Report for: Part 1, (Summarize by ascending dose level, Total). Include baseline values.	SAC [A]
3.0371	All Treated	EG1	Summary of ECG Findings (Part 2 MM)	Report for: Part 2 MM, (Summarize: only for 3.4 MM). Include baseline values.	SAC [A]
3.0372	All Treated	EG1	Summary of ECG Findings (All Treated MM)	Report for: All Treated MM, (Summarize for Total). Include baseline values.	SAC [A]
3.0373	All Treated	EG1	Summary of ECG Findings (Part 2 NHL)	Report for: All Treated MM, (Summarize for Total). Include baseline values.	SAC
3.0390	All Treated	OECG1B	Summary of Worst-case Increases in Fridericia's QTc (Part 1)	Report for: Part 1, (Summarize: by ascending dose level, Total). Include only 'worst-case post-baseline'	SAC [A]
3.0391	All Treated	OECG1B	Summary of Worst-case Increases in Fridericia's QTc (Part 2 MM)	Report for: Part 2 MM, (Summarize: only for 3.4 MM) Include only 'worst-case post-baseline'	SAC [A]
3.0392	All Treated	OECG1B	Summary of Worst-case Increases in Fridericia's QTc (All Treated MM)	Report for: All Treated MM, (Summarize: Total). Include only 'worst-case post-baseline'	SAC [A]
3.0393	All Treated	OECG1B	Summary of Worst-case Increases in Fridericia's QTc (Part 2 NHL)	Report for: Part 2 NHL, (Summarize: Total). Include only 'worst-case post-baseline'	SAC

CONFIDENTIAL

BMA117159

Safety: Tables					
No.	Population	IDSL / Example Shell	Title	Programming Notes	Deliverable [Priority]
3.0400	All Treated	OECG2B	Summary of Worst-case Amount of Increase from Baseline Value in Fridericia's QTc (Part 1)	Report for: Part 1, (Summarize: by ascending dose level, Total). Include only 'worst-case post-baseline'	SAC [A]

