1.0080	All Treated	DM9	Listing of Race (All Treated MM)	Report for sub-population: All Treated MM.	SAC [A]
1.0081	All Treated	DM9	Listing of Race (Part 2 NHL)	Report for sub-population: Part 2 NHL.	SAC
Prior and Concomitant Medications					
1.0620	All Treated	OCM1A	Listing of Concomitant Medications (All Treated MM)	Report for sub-population: All Treated MM.	SAC [A]
1.0621	All Treated	OCM1A	Listing of Concomitant Medications (Part 2 NHL)	Report for sub-population: Part 2 NHL.	SAC

ICH: Listings					
No.	Population	IDSL / Example Shell	Title	Programming Notes	Deliverable [Priority]
Exposure and Treatment Compliance					
1.0090	All Treated	OEX8A	Listing of Exposure Data (All Treated MM)	Report for sub-population: All Treated MM.	SAC [A]
1.0091	All Treated	OEX8A	Listing of Exposure Data (Part 2 NHL)	Report for sub-population: Part 2 NHL.	SAC
1.0100	All Treated	ODMOD10A	Listing of Dose Reductions (All Treated MM)	Report for sub-population: All Treated MM. Include Planned Time.	SAC [A]
1.0101	All Treated	ODMOD10A	Listing of Dose Reductions (Part 2 NHL)	Report for sub-population: All Treated MM. Include Planned Time.	SAC
1.0110	All Treated	ODMOD12A	Listing of Dose Delays (All Treated MM)	Report for sub-population: All Treated MM. Include Planned Time. IDSL standard does not report demographic info. PPD [redacted] to check with PPD [redacted] PPD [redacted] regarding planned time and cycle day. If it is too much programming work to change now, we can keep it as it is.	SAC [A]

ICH: Listings					
No.	Population	IDSL / Example Shell	Title	Programming Notes	Deliverable [Priority]
1.0111	All Treated	ODMOD12A	Listing of Dose Delays (Part 2 NHL)	Report for sub-population: All Treated MM. Include Planned Time. IDSL standard does not report demographic info. PPD [redacted] to check with PPD [redacted] PPD [redacted] regarding planned time and cycle day. If it is too much programming work to change now, we can keep it as it is.	SAC
1.0120	All Treated	ODMOD15A	Listing of Dose Escalations (All Treated MM)	Report for sub-population: All Treated MM. Include Age(y)/Sex/Race, Cycle, Visit. For C2MD, list the dose escalations where a dose escalation is indicated in the data – from the site.	SAC [A]
1.0121	All Treated	ODMOD15A	Listing of Dose Escalations (Part 2 NHL)	Report for sub-population: All Treated MM. Include Age(y)/Sex/Race, Cycle, Visit. For C2MD, list the dose escalations where a dose escalation is indicated in the data – from the site.	SAC

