1.0490	All Treated	ODMOD14A	Listing of Incomplete Infusions (All Treated MM)	Report for sub-population: All Treated MM.	SAC [A]
1.0491	All Treated	ODMOD14A	Listing of Incomplete Infusions (Part 2 NHL)	Report for sub-population: Part 2 NHL.	SAC

CONFIDENTIAL

BMA117159

ICH: Listings					
No.	Population	IDSL / Example Shell	Title	Programming Notes	Deliverable [Priority]
1.0500	All Treated	ODMOD17A	Listing of Infusion Interruptions (All Treated MM)	Report for sub-population: All Treated MM.	SAC [A]
1.0501	All Treated	ODMOD17A	Listing of Infusion Interruptions (Part 2 NHL)	Report for sub-population: Part 2 NHL.	SAC
Adverse Events					
1.0140	All Treated	OAE04	Listing of All Adverse Events (All Treated MM)	Report for population subgroup: All Treated MM. Remove onset cycle and cycle day from all AE related listings.	SAC [A]
1.0141	All Treated	OAE04	Listing of All Adverse Events (Part 2 NHL)	Report for population subgroup: Part 2 NHL. Remove onset cycle and cycle day from all AE related listings.	SAC
1.0150	All Treated	OAE03	Listing of Subject Numbers for Individual Adverse Events (All Treated MM)	Report for sub-population: All Treated MM.	SAC [A]
1.0151	All Treated	OAE03	Listing of Subject Numbers for Individual Adverse Events (Part 2 NHL)	Report for sub-population: Part 2 NHL.	SAC
1.0160	All Treated	AE2	Listing of Relationship Between Adverse Event System Organ Classes, Preferred Terms, and Verbatim Text (All Treated MM)	Report for sub-population: All Treated MM.	SAC [A]
1.0161	All Treated	AE2	Listing of Relationship Between Adverse Event System Organ Classes, Preferred Terms, and Verbatim Text (Part 2 NHL)	Report for sub-population: Part 2 NHL.	SAC

ICH: Listings					
No.	Population	IDSL / Example Shell	Title	Programming Notes	Deliverable [Priority]
Serious and Other Significant Adverse Events					
1.0180	All Treated	OAE04	Listing of Fatal Serious Adverse Events (All Treated MM)	Report for sub-population: All Treated MM. Include column to indicate relationship to study treatment.	SAC [A]
1.0181	All Treated	OAE04	Listing of Fatal Serious Adverse Events (Part 2 NHL)	Report for sub-population: All Treated MM. Include column to indicate relationship to study treatment.	SAC
1.0190	All Treated	OAE04	Listing of Non-Fatal Serious Adverse Events (All Treated MM)	Report for sub-population: All Treated MM. Include column to indicate relationship to study treatment.	SAC [A]

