Hepatobiliary (Liver)					
1.0410	All Treated	MH2	Listing of Medical Conditions for Subjects with Liver Stopping Events (All Treated MM)	Report for sub-population: All Treated MM.	SAC [A]
1.0411	All Treated	MH2	Listing of Medical Conditions for Subjects with Liver Stopping Events (Part 2 NHL)	Report for sub-population: Part 2 NHL.	SAC
1.0420	All Treated	SU2	Listing of Substance Use for Subjects with Liver Stopping Events (All Treated MM)	Report for sub-population: All Treated MM.	SAC [A]
1.0421	All Treated	SU2	Listing of Substance Use for Subjects with Liver Stopping Events (Part 2 NHL)	Report for sub-population: Part 2 NHL.	SAC

CONFIDENTIAL

BMA117159

ICH: Listings					
No.	Population	IDSL / Example Shell	Title	Programming Notes	Deliverable [Priority]
All Laboratory					
1.0330	All Treated	OLB7	Listing of All Laboratory Data for Subjects with Any Value of Potential Clinical Importance (All Treated MM)	Report for sub-population: All Treated MM.	SAC [A]
1.0331	All Treated	OLB7	Listing of All Laboratory Data for Subjects with Any Value of Potential Clinical Importance (Part 2 NHL)	Report for sub-population: Part 2 NHL.	SAC
1.0320	All Treated	OLB13	Listing of Laboratory Data with Character Results (All Treated MM)	Report for sub-population: All Treated MM.	SAC [A]
1.0321	All Treated	OLB13	Listing of Laboratory Data with Character Results (Part 2 NHL)	Report for sub-population: Part 2 NHL.	SAC
1.0350	All Treated	UR2A	Listing of Urinalysis Data for Subjects with Any Value of Potential Clinical Importance (All Treated MM)	Report for sub-population: All Treated MM.	SAC [A]
1.0351	All Treated	UR2A	Listing of Urinalysis Data for Subjects with Any Value of Potential Clinical Importance (Part 2 NHL)	Report for sub-population: Part 2 NHL.	SAC
ECOG Performance Status					
1.0430	All Treated	PS5A	Listing of ECOG Performance Status (All Treated MM)	Report for sub-population: Part 2 NHL.	SAC [A]
1.0431	All Treated	PS5A	Listing of ECOG Performance Status (Part 2 NHL)	Report for sub-population: All Treated MM.	SAC
Response					
1.0560	All Treated	RE5	Listing of Investigator-Assessed Responses (All Treated MM)	Report for sub-population: All Treated MM. List investigator reported response by visit.	SAC [A]

ICH: Listings					
No.	Population	IDSL / Example Shell	Title	Programming Notes	Deliverable [Priority]
1.0561	All Treated	RE5	Listing of Investigator-Assessed Responses (Part 2 NHL)	Report for sub-population: Part 2 NHL. List investigator reported response by visit.	SAC

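### Thirteen displays titled Part 2 NHL in Appendix 12 carry programming notes that select the myeloma population; one myeloma listing has the reverse error, and one study population table contradicts itself

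*SAP*

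**What the plan says.** SAP Section 4 defines two sub-populations of All Treated. The lymphoma one is "Part 2 NHL: all Part 2 lymphoma subjects of All Treated population". The myeloma one is "All Treated MM: comprise of subjects in Part 1 and Part 2 MM", and Part 1 enrolled only myeloma patients. Section 4 then refers the reader to Appendix 12 for the population of each display.

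In Appendix 12 several rows have a title and a programming note that name different cohorts:

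- ICH listing 1.0181 (Section 16.12.13): "Listing of Fatal Serious Adverse Events (Part 2 NHL) Report for sub-population: All Treated MM".
- ICH listing 1.0101 (Section 16.12.13): "Listing of Dose Reductions (Part 2 NHL) Report for sub-population: All Treated MM".
- Safety table 3.0553 (Section 16.12.8): "Summary of Hematologic Toxicity by Preferred Term and Maximum Grade (Part 2 NHL) Report for: All Treated MM, (Summarize: Total".
- Safety table 3.0373 (Section 16.12.8): "Summary of ECG Findings (Part 2 NHL) Report for: All Treated MM, (Summarize for Total".
- ICH listing 1.0430 (Section 16.12.13), in the other direction: "Listing of ECOG Performance Status (All Treated MM) Report for sub-population: Part 2 NHL".
- Study population table 1.0061 (Section 16.12.4): "Summary of Study Populations (NHL) Report for: Part 2 MM, (Summarize: only for 3.4 MM). This table is" based, the note goes on, on subjects enrolled to NHL.

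**The concern.** These notes are operative instructions. In the 13 lymphoma rows the Population column says only All Treated, which covers both diseases. Apart from the title, the note is therefore the one field that picks the cohort, and it picks the wrong one.

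Some of these displays are required by the body of the SAP. Section 8.3 asks for separate subject-level listings of fatal and of non-fatal SAEs. Section 8.4 asks for supporting listings of adverse events leading to discontinuation, to dose interruption or delay, and to dose reduction. Section 6.5 asks for separate listings of dose reductions, escalations and delays. For lymphoma, listings 1.0181 and 1.0191 are the only ones that separate fatal from non-fatal SAEs. Table 3.0553 is the only lymphoma table of hematologic toxicity by preferred term and maximum grade, and table 3.0373 is the only lymphoma table of ECG findings. Run from their notes, those two tables would print myeloma counts over a myeloma denominator under a Part 2 NHL title.

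Section 3.3 allows the myeloma cohort to be reported first under its own database release. The lymphoma displays may then be produced in a later, separate run, so their notes need to be right on their own.

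**Working it through.** The SAP gives no figure to reproduce. The check is a row-by-row comparison of title and note in Appendix 12, followed by a count.

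**Step 1. Do the populations overlap?** By the Section 4 definitions, All Treated MM is Part 1 plus Part 2 MM, all myeloma, and Part 2 NHL is lymphoma only. They share no subject. A display run on All Treated MM therefore contains no lymphoma patient.

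**Step 2. Lymphoma titles with a myeloma note.**

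| Type | Number | Content | Note selects |
|---|---|---|---|
| ICH listing | 1.0101 | Dose reductions | All Treated MM |
| ICH listing | 1.0111 | Dose delays | All Treated MM |
| ICH listing | 1.0121 | Dose escalations | All Treated MM |
| ICH listing | 1.0181 | Fatal SAEs | All Treated MM |
| ICH listing | 1.0191 | Non-fatal SAEs | All Treated MM |
| ICH listing | 1.0201 | AEs, permanent discontinuation | All Treated MM |
| ICH listing | 1.0241 | AEs, dose reduction | All Treated MM |
| ICH listing | 1.0251 | AEs, interruption or delay | All Treated MM |
| ICH listing | 1.0511 | AEs, incomplete infusion | All Treated MM |
| ICH listing | 1.0521 | AEs, infusion interruption | All Treated MM |
| ICH listing | 1.0431 | ECOG status | All Treated MM |
| Safety table | 3.0553 | Hematologic toxicity | All Treated MM |
| Safety table | 3.0373 | ECG findings | All Treated MM |

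Count: 11 listings + 2 safety tables = 13.

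**Step 3. The reverse case.** ICH listing 1.0430, the myeloma ECOG listing, selects Part 2 NHL. The notes of 1.0430 and 1.0431 are simply exchanged.

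**Step 4. The mixed case.** Study population table 1.0061 opens with Part 2 MM, but the rest of its note describes enrolled lymphoma subjects, a No Treatment column and a Part 2 NHL row. The note contradicts itself and does not clearly select myeloma. It brings the rows to correct to 13 + 1 + 1 = 15.

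**Step 5. Intent or slip?** The notes repeat those of the myeloma counterpart. Listing 1.0111 even carries over the internal to-do remark from 1.0110. Nearby lymphoma listings, such as 1.0141, 1.0461, 1.0471 and 1.0541, select Part 2 NHL. The pattern is one of copied text.

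**Step 6. What still reports lymphoma safety correctly?**

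- All adverse events: listing 1.0141.
- SAEs: listing 30.0541 and table 3.0703.
- Deaths: listing 1.0391.
- Discontinuation events: listing 1.0471.
- Dose modifications: tables 1.0253 and 1.0263, and listing 30.0131.
- Hematologic toxicity: tables 3.0543 and 3.0873, and listing 1.0541.
- ECG: tables 3.0383, 3.0393 and 3.0403.
- ECOG: tables 3.0413 and 3.0423.

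**The case against.** The best defense is that a display is specified by its title and its note together. All the titles are right, so each row contradicts itself and does not plainly order a myeloma display. If the notes were followed literally, 1.0181 would duplicate 1.0180 and 3.0553 would duplicate 3.0552 under another title, which quality control should catch. The slip involves no method, endpoint or population definition, and none of the affected lymphoma rows is flagged for the myeloma reporting effort.

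Much of this stands, and it limits the consequence. It does not remove the conflict. The SAP does not say whether title or note governs, and the programmer should not have to guess in a set that includes fatal SAEs. The myeloma deliverable is not untouched either, because listing 1.0430 carries its flag.

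A reader might infer that lymphoma safety reporting as a whole would rest on myeloma patients, or that lymphoma SAEs would disappear from the report. The document does not support this: the displays in Step 6 of the working have correct notes and cover most of the same events. A reader might also count table 1.0061 as a fourteenth lymphoma display set plainly to myeloma. Its note goes on to describe the enrolled lymphoma subjects, so it is better treated as a self-contradiction.

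**Conclusion.** The point holds, confined to the named displays. Thirteen lymphoma displays (11 ICH listings and safety tables 3.0553 and 3.0373) carry a note selecting a population with no lymphoma subject. One myeloma listing, 1.0430, carries the reverse error. One study population table, 1.0061, contradicts itself. Only two of the 13 are numeric safety summaries; in those, both counts and denominators would be wrong if the note were followed.

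The conclusion rests on the Section 4 definitions and on the notes as printed. The consequence depends on the note being followed over the title, which the SAP leaves open. That the notes were copied by mistake is an inference from the neighboring rows.

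**What to change.** In Appendix 12:

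- **ICH listings 1.0101, 1.0111, 1.0121, 1.0181, 1.0191, 1.0201, 1.0241, 1.0251, 1.0511, 1.0521 and 1.0431:** set the sub-population to Part 2 NHL.
- **Safety tables 3.0553 and 3.0373:** report for Part 2 NHL, summarized only for the 3.4 NHL column.
- **ICH listing 1.0430:** set the sub-population to All Treated MM.
- **Study population table 1.0061:** delete the opening reference to Part 2 MM and the 3.4 MM column, and keep the enrolled NHL subjects with the No Treatment column. Do not replace it with Part 2 NHL. That is a subset of All Treated, so enrolled but untreated lymphoma subjects would drop out.

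Each change should say whether it concerns a table or a listing, because study population tables and ICH listings share the 1.xxxx number range (Section 16.12.1). ICH listing 1.0061 is correct and should stay as it is. Tables 1.0101, 1.0111, 1.0121, 1.0191 and 1.0201 are correctly specified Part 2 MM tables.

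The cost is 15 text edits, with no effect on design, data collection or sample size.
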